## BACKGROUND/SCIENTIFIC RATIONALE

---

Social and structural inequities contribute significantly to increasing health disparities globally, with the increasing numbers of migrants throughout the world bearing a disproportionate burden. The immigrant share of the U.S. population has risen steadily over the past four decades, comprising 13.5% of the total population in 2015, with Mexican-born immigrants accounting for 27% of all immigrants. The social, legal, and economic context of the migration process, including increasing uncertainty, discrimination, stigma, lack of access to resources, and fear of deportation and family separation based on immigration policies and public perception of immigrants as a threat all have a critical impact on adverse mental health outcomes among Mexican immigrants in the U.S. In addition, Mexican immigrants have low utilization rates for mental healthcare, in part because of barriers that include lack of health insurance, ineligibility for governmental health programs, discrimination, lack of interpretation services and culturally appropriate care, and an anti-immigrant political and economic climate. Although evidence points to the need to address socio-structural determinants, many mental health interventions offered to Mexican immigrants have focused on individual-level predictors of mental health. Also, Mexican immigrants' health outcomes are often viewed within the Latino health paradox, and therefore are frequently overlooked in mental health research and development of appropriate interventions, despite mounting evidence of mental health disparities and disproportionate exposure to trauma. Thus, multilevel, transdisciplinary intervention approaches that address social-structural determinants of mental health, are culturally appropriate, build upon Mexican immigrants' strengths, are cost-effective and scalable, and occur in non-stigmatized settings are needed.

In prior NIH-funded research, the PI and community partners developed and tested a 6-month community-based advocacy, learning, and social support intervention, which pairs paraprofessional university students with refugee adults to engage in mutual learning and social change efforts. The intervention was found to decrease participants' psychological distress, improve their quality of life, access to resources, social support, and English proficiency, and improve communities' responsiveness to refugees; and also proved to be highly acceptable, cost effective, and sustainable. The goal of this research is to advance the science of community-level mental health interventions that aim to reduce social inequities and health disparities. The proposed study will adapt and integrate a successfully implemented multilevel, ecological intervention that addresses social-structural determinants of mental health into existing efforts at three community partner organizations that focus on mental health, education, legal, and civil rights issues for Latinx immigrants in New Mexico. Using a mixed methods longitudinal design, the processes and outcomes of the collaborative, community-based intervention efforts, including the impact of the quality of the community-based participatory research (CBPR) partnerships on individual, organizational, and community-level outcomes, will be illuminated.

## OBJECTIVES/AIMS

---

The objective of this study is to: a) adapt the intervention for Latinx immigrants (*Immigrant Wellbeing Project; IWP*); b) integrate *IWP* into existing efforts at four community partner organizations; and c) elucidate new understandings of partnership and intervention processes that lead to sustainable multilevel changes and the reduction of mental health disparities and related social inequities.

**Aim 1.** Conduct an in-depth study of the mental health needs, stressors, current political/economic/social context, and local solutions as experienced by 24 Latinx recent and non-recent immigrants and their families residing in Bernalillo County New Mexico and contextualized by staff at four community partner organizations.

**Aim 2.** Building on the data from Aim 1, use a CBPR approach to adapt the intervention model (*IWP*) and integrate it within existing service delivery and social change efforts at four community partner organizations.

**Aim 3.** Using a mixed methods longitudinal design, investigate the feasibility and acceptability of the adapted community-based mental health intervention and test the quality of the CBPR partnership and impact of the intervention on mental health problems and protective factors among 90 Latinx immigrants and on organizational and government changes in policies and practices impacting

immigrant mental health.

**3.1** The *IWP* and collaborative adaptation/integration process will be feasible and acceptable and will serve as a model for implementing and studying multilevel, community-based intervention efforts.

**3.2** *IWP* participants' psychological distress will decrease significantly over time.

**3.3** *IWP* participants' protective factors (access to resources, English proficiency, environmental mastery, social support) will increase significantly over time.

**3.4** Lower levels of psychological distress will be mediated by the protective factors.

**3.5** Qualitative data will document changes in organizational and governmental policies and practices and the context of implementation at each site, explore other impacts, and inform interpretation of quantitative data.

**3.6** Quality of CBPR partnership at each site will be related to policy/practice changes and health outcomes.

## **STUDY DESIGN**

---

### **I. Target Population and Inclusion/Exclusion Criteria**

All Latinx immigrant adults (ages 18 and older) residing in Bernalillo County, NM will be eligible to participate. We will include Latinx immigrants with a wide range of time in the U.S. in order to explore the utility of the *IWP* across recent and non-recent immigrants. This is particularly important given research findings related to the Latino health paradox. Exclusion criteria will be severe cognitive functioning problems, imminent suicide risk, or mental illness that is so severe as to impede participation in a group and that warrants immediate individual treatment. Participants may or may not speak English. The focus of this study is on Latinx immigrants, so it is important to include non-English speaking participants. In addition, the Latinx immigrant participants in the study may or may not have legal documentation for being in the United States. However, we will not ask participants about their legal status, and will take the extra precautions to protect participants' rights and welfare. Organizational staff who participate in interviews will not necessarily be Latinx immigrants, but will be adult staff employed at our three community partner organizations.

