### **III. Recruitment and Screening Procedures**

Recruitment will occur in coordination with the four community partner organizations (Centro Sávila, Encuentro, New Mexico Dream Team, and New Mexico Immigrant Law Center) and will be conducted by the Research Coordinator and RA [name]. Organizations will identify potential participants among those whom they are serving. We do not anticipate using flyers or recruitment materials, but if our partner organizations think that a flyer would be helpful, we will create it with feedback from our partner organizations and submit it to the IRB for approval prior to conducting recruitment. The Research Coordinator and/or [name] will meet in-person with potential participants who are referred by community partner organizations. The study staff member will ensure that the potential participant is a resident of Bernalillo County and an immigrant from Mexico. If the potential participant does not meet these eligibility requirements, he/she will not be enrolled in the study. No data will be collected from potential participants who do not meet eligibility requirements. No data will be collected from potential participants who do not meet eligibility requirements. Exclusion will be based on review of interview data by the PI and [name], therapist and director of Centro Sávila. Excluded adults (except those with cognitive functioning issues already being addressed or those already in treatment) will be referred immediately for individual treatment. Data collected from any excluded adults will be destroyed.

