## VI. *Study Timelines*

The study is funded for almost 5 years (9/23/18-6/30/23). Aim 1 data collection will occur during Year 1 (January-March 2018). Aim 3 intervention and data collection will be implemented in three waves (months 15-20, 27-32, 39-44). Each wave will occur at a different community partner organization and will be adapted and integrated into existing activities and services in different ways, with the goal of creating sustainable, community-level changes by building upon community mobilization/organizing/social change efforts and social networks that are essential components of achieving sustainable, community-level changes. Data collection will end by October 2022.

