***Hypothesis 3.3*** *IWP participants’ protective factors (access to resources, English proficiency, environmental mastery, social support) will increase significantly over time.* Growth curve modeling will be implemented using hierarchical linear modeling (HLM). Analyses will proceed sequentially beginning with baseline ‘intercept-only’ models, then testing fully parameterized model (see Goodkind, et al., 2012 for detailed description of analytic method). If this iterative process identifies that the best fitting model includes significant random effects corresponding to the significant fixed effects (i.e., that there is significant variability in intercepts and/or slopes), we will attempt to model it using level-2 predictors. Level-2 predictors to be tested as potential moderators will include sex, age, length of time in the U.S., and intervention hours, which will allow us to identify relevant individual difference variables (e.g., age) that may predict response to the intervention and to test whether intervention dosage predicts differential change (a finding that would strengthen the inference of treatment effects). Calculating effect sizes for multilevel models is complex; because our focus will be the effect of the intervention over time, we will examine the percentage of variance explained (PVE) by the addition of time to each model by comparing the PVE of the best fit Level 1 model to the Level 1 intercept-only model.

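### The time-in-the-U.S. moderator is pooled over sites and waves with no site or wave term, so it can absorb a site, year or adaptation difference in change; it should be estimated within site

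*Combined protocol and SAP*

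**What the plan says.** - **Purpose of the range.** Target Population and Inclusion/Exclusion Criteria: "We will include Latinx immigrants with a wide range of time in the U.S. in order to explore the utility of" IWP in recent and non-recent immigrants. No cut for recent is defined.
- **Who sets the mix.** Recruitment and Screening Procedures: "Organizations will identify potential participants among those whom they are serving". At referral, "The study staff member will ensure that the potential participant is a resident of Bernalillo County and an immigrant from Mexico". Time in the U.S. is not used to balance enrolment.
- **Sites and waves.** Study Timelines: "Each wave will occur at a different community partner organization", in "three waves (months 15-20, 27-32, 39-44"), and each wave "will be adapted and integrated into existing activities and services in different ways".
- **Analysis.** Data Analysis/Statistical Considerations, under Hypothesis 3.3: "Level-2 predictors to be tested as potential moderators will include sex, age, length of time in the U.S., and intervention hours". These are tried only if the best-fitting model shows "that there is significant variability in intercepts and/or slopes". No site, wave or calendar-year term is named for the growth models.

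**The concern.** With one organization per wave, organization, calendar year and form of adaptation are completely aliased. The plan itself expects sites to matter: Hypothesis 3.6 links partnership quality at each site to health outcomes. The partners described under Study Location(s) offer mental health care, adult education and immigration legal services, so their clients could plausibly differ in time since arrival.

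If both average change and time in the U.S. differ by site, a pooled moderator coefficient mixes two comparisons: newer against longer-settled people within a site, and one site against another. Only the first answers the stated question.

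The planned sequence adds to this. Site differences in change increase the slope variance that triggers the search for moderators, and the named list offers no site term to account for it.

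At stake is the answer to an exploratory question that the protocol gives as a reason for its broad eligibility.

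**Working it through.** The plan states no SD, effect size or power for this comparison, so there is no planned figure to reproduce.

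**Inputs from the documents.** 90 participants in Aim 3; three waves, one organization each; 30 per wave (implied by 30 pairs × 3 waves = 90); wave starts 12 months apart (months 15, 27, 39).

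**Inputs assumed.** The mix of time in the U.S. by site and the spread of mean change between sites. Neither is in the documents.

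**Step 1: what the pooled coefficient estimates.** Write individual change as m + s_j + βx + e, where s_j is the site effect and x is time in the U.S. Let R be the share of the variance of x that lies between sites, and g the slope of s_j on the site mean of x. Then:

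- pooled coefficient: expectation β + R·g
- within-site coefficient: expectation β

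The bias R·g is zero if the mixes are equal (R = 0) or if site effects are unrelated to the site means of x (g = 0).

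**Step 2: the mechanism in numbers.** Take a recent/non-recent split, no true moderation, within-site SD of change 1, and site means of −0.25, 0 and +0.25. R = variance of the three site proportions ÷ (0.5 × 0.5). Bias = mean site effect among recent minus that among non-recent.

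| Recent of 30 per site | R | Bias (SD) | Pooled test significant |
|---|---|---|---|
| 15/15/15 | 0 | 0 | 4.6% |
| 12/15/18 | 0.03 | 0.07 | 5.9% |
| 9/15/21 | 0.11 | 0.13 | 8.5% |
| 6/15/24 | 0.24 | 0.20 | 15% |

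For 6/15/24, the bias is (24 × 0.25 − 6 × 0.25)/45 = 0.10 among recent and −0.10 among non-recent, a difference of 0.20. R is 0.06/0.25 = 0.24. With site indicators the test rejects in about 5% in every row. The site means here were chosen to line up with the mix, so this table shows the mechanism and is not a forecast. Doubling the step between sites doubles the bias and raises the error rate further.

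**Step 3: a range of assumptions.** Simulated trials with 3 sites of 30, no true moderation, individual change SD 0.8, site effects drawn at random, and a two-sided 5% test of x:

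| Site SD | Between-site share of x | Pooled test significant |
|---|---|---|
| 0.1 | 5–20% | about 5–6% |
| 0.2 | 5% | 5.9% |
| 0.2 | 20%, 40%, 60% | 9%, 13%, 17% |
| 0.3 | 20%, 40%, 60% | 13%, 20%, 28% |

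Repeat runs gave similar values, reaching 29% at the top. With fixed site indicators on change the rate was about 5% (0.046 to 0.052 for the 20–60% shares).

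**Step 4: cost of the within-site estimate.** Variance inflation = 1/(1 − R): 1/0.8 = 1.25 at 20%, 1/0.6 = 1.67 at 40%, 1/0.4 = 2.5 at 60%. Interval width grows by √1.25 = 1.12 to √2.5 = 1.58. For a 45 v 45 split, the difference detectable with 80% power at two-sided 5% is (1.960 + 0.842) × √(2/45) = 0.59 SD. For the 6/15/24 mix it becomes 0.59 × √(1/0.76) = 0.68 SD.

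**The case against.** Several points on the other side stand.

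- **The mix is unknown.** No section gives time in the U.S. by organization; a difference is inferred from the type of service. With small site differences or small shares, the error rate barely leaves 5%.
- **One clientele per wave is partly inferred.** Recruitment is coordinated with four organizations, Study Timelines says only where each wave takes place, and Potential Risks describes the intervention as open to any interested immigrant. The text also moves between three and four organizations, which needs reconciling.
- **The simulation is simpler than the plan.** It tests one predictor of change unconditionally. The plan fits four-occasion growth models and tries moderators only after a check on random effects. Its list is also not worded as closed, and it points to a cited paper for method detail.
- **Site context is studied.** Hypothesis 3.5 and the qualitative case studies address implementation at each site. That may help interpretation, but it does not adjust the coefficient.

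A reader might infer that advice on whom IWP suits would rest on this comparison. The documents do not say so: the purpose is to explore, no Aim 3 hypothesis concerns time in the U.S., and the Benefits section ties dissemination to feasibility, acceptability, appropriateness and effectiveness.

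A reader might also infer that each site must enrol fixed numbers of recent and non-recent immigrants. The analysis section does not dichotomise time in the U.S., and a within-site estimate needs only some spread within each wave.

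**Conclusion.** The concern holds as a gap in the moderator analysis. As written, the coefficient for time in the U.S. combines within-site and between-site differences, and the latter cannot be told apart from year or adaptation. The distortion needs two things together: unequal mixes and unequal average change across sites. Under the assumed values, the false-positive rate runs from about 5% (site SD 0.1, small shares) to 29% (site SD 0.3, share 60%). These rates depend wholly on the assumptions.

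Two stronger readings are tempting. One is that the comparison will in fact be between sites; the documents support only that it can be, in part. The other is that adjusting for site differences in average change would not help. It would: fixed site indicators on change give exactly the within-site coefficient. In the growth model this means site crossed with time, since a site term for starting level alone leaves the problem in place.

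**What to change.** In Data Analysis/Statistical Considerations, under Hypothesis 3.3:

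1. Add fixed site/wave indicators crossed with time to the moderator models. Equivalently, centre time in the U.S. and age within site/wave and cross the centred terms with time.
2. Base any statement on moderation by time in the U.S. on the within-site coefficient. If a between-site coefficient is shown, present it as description only.
3. Report the distribution of time in the U.S. by site.
4. Label the comparison exploratory.

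Optionally, Recruitment and Screening Procedures could ask for a spread of time in the U.S. within each wave. This helps precision, but the analysis change does not depend on it.

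The cost is a few sentences of plan text and a wider interval, with variance about 1.25 to 2.5 times larger if sites explain 20% to 60% of time in the U.S. Nothing is lost in precision if the mixes turn out equal. No new data are needed.

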### **II. Participant Enrollment**

24 Latinx immigrant adult participants will be enrolled in Aim 1.

90 Latinx immigrant adult participants will be enrolled in Aim 3 to participate in the intervention and 4 interviews each.

6 organizational staff will be enrolled in Aim 3 to complete 2 qualitative interviews each.

### **III. Recruitment and Screening Procedures**

Recruitment will occur in coordination with the four community partner organizations (Centro Sávila, Encuentro, New Mexico Dream Team, and New Mexico Immigrant Law Center) and will be conducted by the Research Coordinator and RA [name]. Organizations will identify potential participants among those whom they are serving. We do not anticipate using flyers or recruitment materials, but if our partner organizations think that a flyer would be helpful, we will create it with feedback from our partner organizations and submit it to the IRB for approval prior to conducting recruitment. The Research Coordinator and/or [name] will meet in-person with potential participants who are referred by community partner organizations. The study staff member will ensure that the potential participant is a resident of Bernalillo County and an immigrant from Mexico. If the potential participant does not meet these eligibility requirements, he/she will not be enrolled in the study. No data will be collected from potential participants who do not meet eligibility requirements. No data will be collected from potential participants who do not meet eligibility requirements. Exclusion will be based on review of interview data by the PI and [name], therapist and director of Centro Sávila. Excluded adults (except those with cognitive functioning issues already being addressed or those already in treatment) will be referred immediately for individual treatment. Data collected from any excluded adults will be destroyed.

#### IV. *Informed Consent Process*

Latinx immigrant participants will read a consent form that explains the nature and purpose of the interview and/or intervention, ensures confidentiality, describes the participant compensation, and makes clear that participation is completely voluntary and may be terminated at any time. Participants will be made aware that they are free not to answer any question and/or to stop at any time without negative consequence. Each potential participant will be provided the consent form in Spanish or English (whichever they prefer) in advance of the interview. The consent form will also be read aloud to each potential participant, since some participants may not be literate. The consent form will be explained in detail, emphasizing the individual's right to choose not to participate. It will be clearly stated that the individual will not be penalized in any way for choosing not to participate, and refusal to participate will in no way affect the individual's access to services at the community organization which is coordinating recruitment or any services to which he or she is otherwise entitled. Next, each potential participant will be asked if they have any questions regarding the study. Each potential participant will be given adequate time to consider whether they want to participate in the study. The participants will then verbally indicate their consent (which will be documented by signature of study team member but will not require the participant's signature in order to protect confidentiality) and will be given a copy of the consent form to keep before the interview begins. A **waiver of consent documentation (no signature)** is being requested because a signed consent form would be the only record linking the participant and the study, and breach of confidentiality would be the principal risk, due to the potential situation in which some participants may not have legal status in the United States.

Organizational staff participants will be read and asked to sign a consent form that explains the nature and purpose of the interview, ensures confidentiality, describes the participant compensation, and makes clear that participation is completely voluntary and may be terminated at any time. Participants will be made aware that they are free not to answer any question and/or to stop at any time without negative consequence. Each potential staff participant will be provided the consent form in advance of the interview. Each potential staff participant will be asked if they have any questions regarding the study. Each potential staff participant will be given adequate time to consider whether they want to participate in the study.

**HIPAA Authorization:** N/A

**Non-English Speaking Participants:** We expect that all participants in the study will complete informed consent and interviews in Spanish (their native language). The consent process will be conducted in Spanish by a Spanish-speaking member of the research team (either the Research Coordinator or RA [name]). The consent form and all interview guides will be translated by two study team members ([name] and co-I [name]) and back-translated by two study team members (Research Coordinator and co-I [name]), and differences will be reconciled through in-person discussion of any discrepancies. The Spanish language consent form and interview guides will be submitted to the IRB for approval prior to study enrollment.

**Cognitively Impaired Adults/ Use of a Legally Authorized Representative (LAR):** N/A

